- 1. Protocol Title:** Paravertebral Block Versus Pectoral Nerve Block for Analgesia Following Mastectomy
- 2. Investigator(s):** [name] MD, [name], [name], [name], [name], [name], [name] and [name]
- 3. Version Date:** March 30, 2018
- 4. Objectives:**
 - I. Primary Objective: To determine if pectoral nerve blocks (PECs) achieve equal analgesia following mastectomy, partial mastectomy or lumpectomy, with and without reconstruction, when compared to paravertebral blocks (PVBs).
 - II. Secondary Objective: To trend complication rates for PECs and PVBs.

5. Background:

Postoperative pain control is essential following any major operative procedure. A variety of methods have been utilized to ensure adequate analgesia, each with its own advantages and risks. Increasingly, attention has focused on regional methods of analgesia, which may allow for reduction in systemic narcotic use and their associated complications [1]. Proposed benefits of regional analgesia and a resultant reduction in narcotic use include decreased risk of cancer progression, decreased length of stay, and decreased risk of ileus.

The most common regional block used to achieve postoperative analgesia following mastectomy is the paravertebral block, during which local anesthetic is injected into the paravertebral space which contains the thoracic spinal nerves, between the costotransverse ligament and the pleura. At our institution there has been recent interest in an alternative regional block. The pectoral nerve block is performed by injecting anesthetic between the pectoralis major and the pectoralis minor (PECs I) or between the pectoralis minor and the serratus anterior (PECs II) [2]. A serratus plane block is a modification of the PEC block, in which a local anesthetic is injected between the serratus anterior and latissimus dorsi muscles.

The proposed advantage of the pectoral nerve block for regional anesthesia during breast surgery is equal analgesic efficacy with fewer potential complications.

6. Setting of the Research:

The study will take place at Spectrum Health Medical Center: Butterworth Hospital and Spectrum Health Blodgett Hospital with follow up through Spectrum Health Lemmen-Holton Cancer Pavilion and the Lake Drive locations.

7. Resources Available to Conduct this Research:

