Patients will be referred by the Spectrum Health breast surgeons. If the patient is interested, the investigator or research staff will provide a copy of the informed consent for the patient to review. Spectrum Health research staff will then follow up with the patients to further discuss the study and confirm that the patient is interested in participation.

Patients will then be consented by a clinical research coordinator. Typically, this would occur at the hospital where they will be undergoing their surgery. The coordinator will review the consent with the patient (and family or significant other, as applicable) and have the patient sign it. The coordinator will make all reasonable attempts to keep the discussion as private as possible. In order to minimize coercion, it will be made very clear to patients that their participation is strictly voluntary and that not choosing to participate will in no way affect their present or future care at Spectrum Health.

Once the patient has been randomized to either PEC or PVB, the anesthesiologist on call for local blocks will see the patient and review that analgesic plan and the risks of that specific procedure with the patient. This meeting and explanation are standard, but they may also answer questions the patient may have related to the study.

We anticipate enrolling 128 total patients in the study, 64 in the PVB arm and 64 in the PEC arm.

There will be no payment to patients for inclusion in the study.

b. Inclusion and Exclusion Criteria

Inclusion Criteria:

- i. Female patients \geq 18 years of age
- ii. Total mastectomy or partial mastectomy with or without reconstruction OR planned lumpectomy.
- iii. Patient determined by their surgeon as medically able to receive a regional block for post-operative analgesia
- iv. Patient agrees to participate in the study and signs informed consent

Exclusion Criteria:

- i. Neoadjuvant radiation therapy
- ii. Stage IV cancer
- iii. Planned general anesthesia use during surgery
- iv. Allergies to ropivacaine, midazolam, fentanyl, or propofol
- v. Pregnant women
- vi. Prisoners
- vii. Adults unable to consent
- viii. Non-English-speaking patients

c. Study Endpoints

Primary Outcome Variables:

Intraoperative narcotic use, Post Anesthesia Care Unit (PACU) narcotic use and postoperative narcotic use. We would expect that all variables will have a lower values in patients randomized to PEC versus PVB.

Secondary Outcome Variable(s):

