Data to be collected are detailed in Appendix B (pdfs of REDCap database for this study). Data will be managed by Spectrum Health research staff and kept in a locked cabinet or a limited-access electronic drive.

f. Provisions to Monitor the Data for the Safety of Subjects

The Principal Investigator will oversee the safety of the study. This safety monitoring will include careful assessment and appropriate reporting of adverse events (see "Adverse Events" below).

g. Withdrawal of Subjects

A patient may be withdrawn from the study prior to the expected completion of that subject for failure to adhere to protocol requirements. Patients may choose to withdraw from the study at any time. Data that have already been collected on these patients will still be used.

The primary investigator may remove a patient at any time from this research study if it is felt to be in the best interest of the patient.

9. Statistical Plan:

a. Sample Size Determination

The primary outcome variable for this study is the difference in narcotic use between the PEC group and the PVB group during the first 24 hours following surgery. If we define a clinically important effect as the mean narcotic use in the PVB group is twice that seen for the PEC group, with a standard deviation equal to the mean of the PVB group, with $\alpha=0.05$ and $\beta=0.20$, we will be able to detect a statistically significant difference with 64 subjects in each group, using the unpaired t-test. Complication rates will also be compared between the two

groups, although with an anticipated rate of only 5% in the PVB group, it is unlikely with the projected sample size that we will find a statistically significant effect for this variable.

b. Statistical Methods

Summary statistics will be calculated. Quantitative data will be expressed as the mean + SD, while nominal data will be expressed as a percentage. Comparisons between groups for quantitative variables will be performed using the t-test. Nominal variables will be evaluated using the Chi-Square test. The data will be analyzed as intention to treat. Significance will be assessed at $p<0.05$.

10. Risks to Subjects:

Risks of both procedures are very low – less than 5% for each risk listed here.

PEC

- a. Vascular puncture
- b. Inadequate analgesia
- c. Intraneuronal injection, resulting in transient neuropathy
- d. Incomplete nerve block
- e. Infection

PVB

- a. Pneumothorax
- b. Vascular puncture
- c. Incomplete nerve block

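### One unadjusted t-test pools lumpectomy with mastectomy, so a block disadvantage confined to mastectomy could be diluted, and no estimate by operation is planned to show it

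*Combined protocol and SAP*

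**What the plan says.** The title of the combined protocol and SAP is "Paravertebral Block Versus Pectoral Nerve Block for Analgesia Following Mastectomy". The primary objective (section 4) is wider: it asks whether pectoral nerve blocks (PEC) "achieve equal analgesia following mastectomy, partial mastectomy or lumpectomy, with and without reconstruction", compared with paravertebral blocks (PVB). Inclusion criterion ii agrees with the objective: "Total mastectomy or partial mastectomy with or without reconstruction OR planned lumpectomy".

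Section 9a defines the primary outcome as the "difference in narcotic use between the PEC group and the PVB group during the first 24 hours following surgery". It sizes the trial on one set of assumptions for the whole population. The effect to be detected is that "the mean narcotic use in the PVB group is twice that seen for the PEC group". The SD is taken to be as large as the PVB mean. Section 9b gives the analysis: "Comparisons between groups for quantitative variables will be performed using the t-test".

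Randomization is 1:1, and no stratification factor is described. The data list under Procedures Involved in the Research includes the operation performed (item iii), but section 9b makes no use of it. There is no limit on the number of lumpectomies.

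**The concern.** The objective lists several operations and asks about equality across them. One average over all of them cannot show that equality holds in each. If lumpectomy patients need less narcotic, or the blocks differ less in them, they pull the pooled difference toward zero. The spread between operations also enlarges the pooled SD. Both effects make a non-significant result more likely.

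That matters more here than in an ordinary superiority trial. The stated aim is equality, and the plan has no margin, so a non-significant difference is likely to be read as success. Under a title that names mastectomy, it would be read as success in mastectomy, with no planned mastectomy estimate to check it against.

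**Working it through.** **The plan's own figure.** From section 9a, set the PVB mean to 1. The PEC mean is then 0.5, the difference 0.5 and the SD 1, so d = 0.5. With two-sided α = 0.05 and 80% power, the normal approximation n = 2(1.960 + 0.842)²/0.5² gives 63 per arm. The exact noncentral t gives 79.5% power at 63 and 80.1% at 64. The stated 64 per arm reproduces, for a single homogeneous population.

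**Assumptions for the dilution check (none is in the documents).**
- Mastectomy: PVB mean 1, PEC mean 1.5, SD 1 in both arms. This is a PEC disadvantage of 0.5 SD, the size of section 9a's effect in the opposite direction.
- Lumpectomy: mean q and SD q in both arms, with q = 0.10 or 0.25. The blocks do not differ.
- Lumpectomy share L is the same in both arms.

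**Formulas.**
- Pooled difference = 0.5(1 − L).
- Variance in one arm = (1 − L)(1² + μ²) + L(q² + q²) − [(1 − L)μ + Lq]², with μ = 1 for PVB and 1.5 for PEC.
- Pooled SD = square root of the mean of the two arm variances.
- Power from the noncentral t at 64 per arm.

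**Worked case, L = 0.5, q = 0.10.**
- PVB variance: 0.5(2) + 0.5(0.02) − 0.55² = 0.7075.
- PEC variance: 0.5(3.25) + 0.5(0.02) − 0.80² = 0.995.
- Pooled SD: √0.85125 = 0.923.
- d = 0.25/0.923 = 0.271, power 33.1%.

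| Lumpectomy share | Pooled power, q = 0.10 | Pooled power, q = 0.25 | Mastectomy per arm | Power, mastectomy alone (d = 0.5) |
|---|---|---|---|---|
| 10% | 70% | 71% | 57.6 (expected) | 76% |
| 25% | 55% | 57% | 48 | 68% |
| 50% | 33% | 35% | 32 | 50% |

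**Equal SD in both operations.** With SD 1 throughout and no difference in lumpectomy, d = 0.5(1 − L). Power is 56% at L = 25% and 29% at L = 50%. Low lumpectomy use is therefore not needed for dilution; a smaller block difference in lumpectomy is enough.

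**Same relative effect in both operations.** Now let PEC use be 50% higher in lumpectomy too (PEC mean 1.5q, SD still q). At L = 0.5 the pooled difference is 0.25 + 0.25q.
- q = 0.10: 0.275/0.913 = 0.301, power 39%.
- q = 0.25: 0.3125/0.872 = 0.359, power 52%.
- q = 0.50: 0.375/0.852 = 0.440, power 69.5%.

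Mastectomy alone still has 50%. The pooled test is worse only at the lowest q.

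**Stratifying the overall estimate.** Return to no difference in lumpectomy, at L = 0.5. The within-procedure SD is √[(1 − L) + Lq²], which is 0.711 at q = 0.10 and 0.729 at q = 0.25. Power for the 0.25 difference is 51% and 49%, against 33% and 35% unadjusted.

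**Precision.** The 95% CI half-width is t × √(2/n) in SD units: 1.979 × √(2/64) = 0.35 at 64 per arm, and 1.999 × √(2/32) = 0.50 at 32 per arm. For the interaction at L = 0.5, the standard error is √[(2/32)(1 + q²)] = 0.251 to 0.258. A true interaction of 0.5 is then 1.99 to 1.94 standard errors, or about 50% power.

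**The case against.** The strongest reply is that the pooled population is the one the trial set out to study. A reader might infer from the title that lumpectomy lies outside the question. The primary objective names it and inclusion criterion ii agrees, so pooling answers a stated question and broad eligibility is a legitimate choice. This stands, and what is left of the mismatch is a title narrower than the objective.

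A reader might also infer that lumpectomy patients cannot show a difference between blocks. The documents do not support that. They report no narcotic use by operation. Intraoperative narcotic is among the listed primary outcomes, and surgery is planned under sedation with added fentanyl as needed, so an inadequate block could show in a lumpectomy too. It follows that the claim that the mastectomy patients alone carry more information than the whole sample is not general. It holds when the blocks do not differ in lumpectomy, but not throughout the range when the relative effect is shared.

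Third, the missing margin is the larger route to a false claim of equality. With no lumpectomies at all, 64 per arm would give a non-significant result 20% of the time for a true 0.5 SD disadvantage and 71% of the time for 0.25 SD. This stands, and estimates by procedure do not cure it. Equally, a margin applied only to the pooled mean could still pass a block that is worse in mastectomy alone.

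**Conclusion.** The point holds in a limited form. Section 9b yields one unadjusted comparison over all operations and no mastectomy estimate, so a null result could not by itself support equality in mastectomy.

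The loss of power depends on an unknown case mix and on how far the block difference shrinks in lumpectomy. With no difference there and lumpectomy use at 10-25% of mastectomy use, the shortfall against mastectomy patients alone is about 5 to 6 percentage points at a 10% lumpectomy share, 11 to 13 at 25% and 15 to 17 at 50%. With a shared relative effect it can vanish or reverse.

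Two stronger conclusions are not supported. One is that accounting for procedure in the overall analysis would not help: in the same scenario it recovers nearly all the lost power at a 50% share, although the overall estimate remains an average over operations. The other is that every mastectomy conclusion must rest on the subgroup alone: with a CI half-width near 0.5 SD, as large as the disadvantage assumed, that estimate is supportive evidence and not a decisive test. This is an inexpensive improvement to the plan, not a flaw that invalidates the pooled comparison.

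**What to change.** In section 9b:

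- Make the overall PEC-PVB estimate stratified by planned procedure, recorded before randomization. The two groups are lumpectomy or partial mastectomy, and total mastectomy with or without reconstruction. State explicitly where partial mastectomy with reconstruction belongs, since criterion ii allows it.
- Pre-specify, as supportive estimates, the PEC-PVB difference with 95% CI in each group and a block-by-procedure interaction estimate with its CI.
- State that equality specifically for mastectomy will not be claimed from the pooled result alone.

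The cost is SAP wording and a few table rows, with no change in sample size or care. Planned procedure may need a data field, because the data list names only the operation performed. The mastectomy CI will be wider, about ±0.50 SD at 32 per arm against ±0.35 SD at 64, and the interaction will be imprecise. The absence of an equivalence or non-inferiority margin has to be dealt with separately.

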Length of operation, estimated blood loss, incidence of postoperative nausea, subjective pain at two weeks (including patient's overall pain rating for the previous two weeks, the patient's stated last time they used pain pills) and number of calls to physician's office following hospital discharge.

d. Procedures Involved in the Research

This is a prospective, randomized study.

Following satisfaction of the inclusion/exclusion criteria and signed informed consent, patients will be randomized to paravertebral block or a pectoral nerve block. The randomization schedule will be set-up prior to study start using an Excel spreadsheet. Spectrum Health statisticians designed the randomization schedule to meet significance for the endpoints. Randomization is 1:1, PEC:PVB. If the patient is unwilling to be randomized to one or the other type of block, they will not be able to participate in the study. After each patient is consented, the randomization schedule will be checked and the data sheet with the type of block to be used will be placed in

the patient chart. The research coordinator will notify anesthesia of which block will be used on the patient.

Patients will proceed to surgery per usual standard of care. The PVB is performed along the spine utilizing ultrasound guided technique. The PEC is performed anteriorly, at the level of the axillary line, also utilizing ultrasound guided technique. Each block will be performed using 20-30 mL 0.5% Ropivacaine¹ per side. Midazolam and fentanyl will be used for sedation as needed. Intraoperatively, patients will undergo monitored anesthesia care with a propofol infusion (50-150 mcg/kg/min). Additional IV fentanyl will be given as needed. Anesthesia will be converted to general anesthesia if the patient is unable to tolerate the procedure with sedation and block anesthetic or if general anesthesia is preferred by the surgeon. This will not disqualify the patient, but the conversion will be noted in REDCap.

¹Package inserts for these FDA-approved drugs are included as Appendix A to the protocol.

All post-operative care will be standard of care.

Data collected will include the following:

- i. Demographics¹
- ii. Medical history²
- iii. Surgical procedure performed & pain control technique(s) used
- iv. Extra doses of narcotic and sedative medication used during surgery.³
- v. Length of surgery
- vi. Duration of hospital stay (measured in minutes)

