The study investigators (Spectrum Health Breast Surgeons) will introduce the study to the patients at their pre-surgery visit. They will fill out and sign an eligibility checklist for the research coordinators. The research coordinators will then reach out to the patient to confirm interest in the study and will give the patient a copy of the informed consent, if they have not already received one. The coordinator will then review the consent with the patient and family (as applicable). Adequate time will be allotted for the patient and/or family and friends to ask questions. Enough time will also be allowed for both the patient and the coordinator to feel that there is an adequate understanding of the study and the responsibilities involved. Subjects will be informed that the research study is voluntary. If the patient is still interested, they will sign a copy of the research consent. A copy of the consent will be given to the patient and a copy will be placed in their medical chart. On the morning of surgery, when the anesthesiologist comes in to discuss anesthesia and pain control with the patient, he or she will also discuss the research study with the patient.

17. Vulnerable Populations:

This study will not include any vulnerable populations.

18. *Sharing of Results with Subjects:*

There are no plans to share study results with the research subjects.

19. References:

1. Glissmeyer, Johnson, Sherman, et al. Effect of paravertebral nerve block on narcotic use after mastectomy. *American Journal of Surgery*. 2015. article in press
2. Wahba, Kamal. Thoracic paravertebral block versus pectoral nerve block for analgesia after breast surgery. *Egyptian Journal of Anaesthesia*. 30.129-135. 2014.
3. Sopena-Zubiria, Fernandez-Mere, Arias, et al. Thoracic paravertebral block compared to thoracic paravertebral block plus pectoral nerve block in reconstructive breast surgery. *Revista Espanol De Anestesiologia Y Reanimacion*. 2012 Jan; 59(1): 12-7
4. Bashandy, Abbas. Pectoral nerves I and II blocks in multimodal analgesia for breast cancer surgery: a randomized clinical trial. *Regional Anesthesia and Pain Medicine*. 2015 Jan; 40(1): 68-74

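### Suitability for both blocks is not confirmed before randomization, so unsuitability for the assigned block can surface after allocation, possibly unevenly between arms

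*Combined protocol and SAP*

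**What the plan says.** **Eligibility.** Section 8b, inclusion iii: "Patient determined by their surgeon as medically able to receive a regional block for post-operative analgesia". No criterion addresses PVB and PEC separately. Section 16 has the breast surgeons introduce the study at the pre-surgery visit and says of them: "They will fill out and sign an eligibility checklist for the research coordinators". The schedule of events marks eligibility at the pre-surgery visit only and randomization on the day of surgery.

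**Anesthesiologist review.** The recruitment text before section 8b says: "Once the patient has been randomized to either PEC or PVB, the anesthesiologist on call for local blocks will see the patient". The purpose is to "review that analgesic plan and the risks of that specific procedure with the patient". Section 10 adds that the anesthesiologist discusses block risks before surgery and that a separate routine-care consent form covers them. Section 16 also mentions a contact "On the morning of surgery, when the anesthesiologist comes in to discuss anesthesia and pain control with the patient", without placing it before or after randomization.

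**Willingness.** Section 8d: "If the patient is unwilling to be randomized to one or the other type of block, they will not be able to participate". Section 12 promises a thorough discussion of risks and benefits with potential subjects.

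**After allocation.** Section 9b specifies intention to treat. Section 8g allows withdrawal for not adhering to the protocol, or by the investigator in the patient's interest, and keeps data collected up to then. Nothing says what happens if the assigned block is found unsuitable or is declined.

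**The concern.** A randomized comparison of two blocks is cleanest when every patient could receive either one at the moment of allocation. Here the check before allocation is generic and made by the surgeon. The block-specific check by the specialist follows allocation and looks at one block only. A patient suitable for PEC but not for PVB can satisfy inclusion iii as worded. She would be noticed if allocated to PVB and might pass unnoticed if allocated to PEC.

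Three consequences are possible:

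- She switches to the other block and is analyzed as randomized, which dilutes the contrast.
- She receives no block, which could raise narcotic use in her arm.
- She is withdrawn before the block, so no narcotic outcome has been collected and she drops out of the primary comparison.

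Dilution deserves care in this trial because the primary objective in section 4 is to show equal analgesia, and a weakened contrast could be taken for equality.

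**Working it through.** **1. Order of events.** Read together, sections 8b, 8d and 16 give: surgeon's checklist, study consent, look-up of the randomization schedule, notice to anesthesia. The recruitment text then puts the anesthesiologist's visit after randomization. No step before the look-up asks about each block.

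**2. Could cases be unequal between arms?** Section 8d places PVB along the spine and PEC anteriorly. The section 10 risk lists give pneumothorax, and hypotension from intrathecal or epidural spread, under PVB and not under PEC. Section 11 presents PEC as potentially reducing both. Against this, a sentence under Adverse Events in section 10 attributes both events to PEC. It conflicts with the lists and with section 11, and the text must be reconciled. Unequal cases are therefore a plausible inference, with no rate behind it.

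**3. Reproduce the sample size (section 9a).** Inputs: PVB mean twice the PEC mean, SD equal to the PVB mean, α = 0.05, β = 0.20. Set the PVB mean to 1, so the PEC mean is 0.5 and the SD is 1.

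- Standardized difference: (1 − 0.5)/1 = 0.50.
- The two-sided t-test needs 63.77 per arm, rounded up to 64. Power at 64 is 0.801. One-sided testing would need 51, so the plan is implicitly two-sided.

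The stated 64 per arm reproduces and leaves almost no reserve.

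**4. Switching, analyzed as randomized (x is an assumption).** If a share x of the PVB arm receives PEC and responds as PEC patients do, the PVB-arm mean is (1 − x)·1 + x·0.5 = 1 − 0.5x. The difference is (1 − 0.5x) − 0.5 = 0.5(1 − x), with the SD held at 1.

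| Assumed x | Difference (SD) | Power at 64 per arm | Per arm for 80% power |
|---|---|---|---|
| 0% | 0.500 | 0.801 | 64 |
| 5% | 0.475 | 0.760 | 71 |
| 10% | 0.450 | 0.714 | 79 |
| 15% | 0.425 | 0.665 | 88 |
| 20% | 0.400 | 0.612 | 100 |

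**5. No block received.** If a share y of the PVB arm has no block and uses k times the PVB mean, the difference becomes 0.5 + y(k − 1). For k above 1 it widens. The direction is therefore not fixed.

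**6. Loss from the PVB arm only (assumed rates).** Losing 5%, 10% or 20% gives power 0.791, 0.780 or 0.753, so precision suffers little. Selection is a separate matter. Suppose the affected type is 10% of patients, uses 50% more narcotic, and remains only in the PEC arm. The PEC mean rises by 10% × 50% = 5%, that is 0.05 × 0.5 = 0.025 SD, against a planned 0.50. Both inputs are assumptions, and the direction follows from them.

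**The case against.** **Refusal is already largely handled.** A reader might infer that unwillingness goes unscreened until after allocation. The documents do not support that. Section 8d excludes anyone unwilling to have either block, section 12 promises a risk discussion, and study consent precedes randomization. Only residual refusal at the later block consent remains. The study consent form is not available here, so how fully it describes each block cannot be judged.

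**The wording may be read sensibly in practice.** Section 5 calls PVB the most common block after mastectomy, so a surgeon may well have PVB, or both blocks, in mind, and the unseen checklist may be more specific. This is fair. It lowers the likely frequency but does not put the requirement into the protocol.

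**A difference between arms is not demonstrated.** A reader might take it as a fact. No rate of unsuitability or refusal is given for either arm, and section 10 puts each listed risk below 5% for both blocks. Those are complication risks, not unsuitability rates, so they neither confirm nor exclude an imbalance.

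**The direction of harm is not settled.** It is tempting to say that the flaw favors a finding of equality. Switching does pull the arms together, but section 8c expects lower narcotic use with PEC, so dilution works against that expectation, and patients left without a block could widen the gap.

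**Intention to treat is already specified.** That stands for patients who remain in follow-up. It does not protect against withdrawal before the block, because section 8g keeps only what has been collected.

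**Conclusion.** The concern holds as a gap in sequence and wording. Suitability for both blocks is not required before allocation, the block-specific review is described as following it, and no rule covers what happens next. Cases could plausibly be unequal between arms, but the documents do not show that they will be.

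The size is illustrative only. Power of about 0.76, 0.71 or 0.67 requires 5%, 10% or 15% of the PVB arm to switch to PEC, no switching the other way, full PEC response in those who switch, and an unchanged SD. If few or no patients are affected, the planned 0.80 is essentially intact. Loss from one arm costs little power; its selection bias cannot be estimated from the documents. The change is worth making because it is cheap, not because serious harm has been shown.

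**What to change.** - **Section 8b, inclusion iii.** Reword along these lines: *Before the allocation is looked up, an anesthesiologist on call for blocks has confirmed that the patient is medically suitable for both PVB and PEC, and the patient has reconfirmed that she is willing to have either.* The suitability judgement itself stays with the clinician.
- **Section 8d and the schedule of events.** Place this check on the day of surgery, before randomization. Section 8d currently ties the look-up to consent, which may take place on an earlier day, so it should tie the look-up to this check.
- **Recruitment text before section 8b.** Amend the sentence on the anesthesiologist's visit to match the new order.
- **Section 8g.** State that a patient who does not receive the assigned block is not withdrawn from the study for that reason, and that her narcotic outcomes are collected and analyzed in her randomized arm.
- **Section 10.** Reconcile the Adverse Events sentence on pneumothorax and hypotension with the risk lists and section 11.

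**Cost.** Protocol wording and a checklist line. Randomization and an anesthesiologist contact already fall on the day of surgery, so the change is mainly one of order. The conversation must cover both blocks, the allocation is known slightly later that morning, and a few patients will be screened out that day.
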